5. STATISTICAL METHODS

Descriptive statistical methods will be used to summarize the data from this study, with confidence intervals calculated for the primary and secondary efficacy endpoints. The term "descriptive statistics" refers to number of subjects (n), mean, median, standard deviation (SD), minimum, and maximum for continuous data and frequencies and percentages for categorical data. The term "treatment group" refers to randomized treatment assignment: active-test, active-reference, and placebo. All data collected during the study will be included in data listings. The data will be sorted first by subject number, and then by date within each subject number. Unless specified otherwise, all statistical testing will be two-sided and will be performed using a significance (alpha) level of 0.05.

All statistical analyses will be conducted with the SAS[®] System, version 9.4 or higher within a validated statistical computing environment.

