6.2 Study Drug Accountability

The Sponsor will supply sufficient quantities of the study drug for the completion of this study.

The study pharmacist or designated study personnel will maintain a Drug Receipt Log and a Subject Study Drug Accountability Log itemizing all study drug received, dispensed to and returned from each subject during the study. All dispensed tubes must be accounted for, and any discrepancies explained. Study site should contact site Clinical Research Associate (CRA) in case of any dispensing errors or if discrepancies are discovered.

Prior to site closure and at appropriate intervals during the study, site CRA will perform study drug accountability and reconciliation. At the end of the study, the Investigator will retain all the original documentation regarding study drug accountability, return, and copies will be sent to the Sponsor.

All unused and used Study Drug tubes will be returned to the Sponsor or its designee for destruction at the end of the study.

7 Study Procedures and Schedule of Events

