3.2. Randomization

This is a double-blind study, thus all site staff, study monitor, and subjects will be blinded to the randomization scheme except for the Unblinded Site Personnel/ designee and Unblinded Monitor. Furthermore, the randomization scheme will be retained by the Drug Depot and will only be shared with Unblinded Site Personnel or designee.

The actual treatment given to individual subjects is determined by a computerized block randomization scheme prepared by an independent third party. The independent third party will prepare the randomization list and hold it throughout the conduct of the study. Subjects are randomized on a 3:3:1 basis (test drug: active comparator: placebo) and stratified by clinical site.

After signing the Informed Consent, each subject will be assigned a unique subject number. Subjects are identified using subject initials, subject number, and date of birth. The subject numbers will be generated by the EDC and assigned sequentially in the order in which subjects are consented at each center.

If a subject discontinues from the study, the subject number and randomization number are not to be reused, and the subject is not allowed to re-enter the study.

The randomization scheme for treatment allocation will be used for statistical and reporting purposes. A copy of the randomization assignment will be retained at each clinical site by unblinded personnel and will be available to FDA or other regulatory agency investigators at the time of site inspection to allow for verification of the treatment identity of each subject.

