3.4.3. Definitions and Terminology

Treatment Day 1 (Baseline)

Treatment Day 1 is the day that study treatment is first initiated.

Study Day

Study Day is defined relative to study treatment initiation (Study Day 1). Thus, the study day of an event is calculated as:

Study
$$Day = event date - date of Study Day 1 + 1$$
.

Days on Study

Days on Study is the number of days from Study Day 1 to the date of study completion or early termination as recorded on the study termination eCRF.

End of Treatment

For efficacy assessments, end of treatment is defined as the last non-missing assessment taken prior to discontinuation of study treatment.

Concomitant Medications

Concomitant medications are those medications taken on or after the initiation of study treatment. This definition includes prescription and all over-the-counter (OTC) medications and all dietary supplements.

CONFIDENTIAL

Previous medications are those medications taken within the 30 days and stopped prior to the initiation of study therapy.

Treatment-Emergent Adverse Event

A treatment-emergent adverse event is defined as any adverse event occurring on or after the initiation of study treatment. For the purpose of defining treatment-emergent adverse events, it is assumed that an adverse event which was reported to have started on Treatment Day 1 without an associated onset time may have occurred after the initiation of study treatment. Hence, adverse events occurring on Treatment Day 1 are assumed to be treatment-emergent.

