4. ANALYSIS POPULATIONS

The populations defined for analysis will include the modified intent-to-treat (mITT), per-protocol (PP), and the safety population.

Safety Population includes all subjects who were randomized and dispensed treatment. This is the population that will be used for the safety assessments.

Modified Intent-to-Treat (mITT) Population includes all Index subjects who met all inclusion/exclusion criteria, were randomized, dispensed treatment, and had at least one post-treatment efficacy evaluation. This is the primary population for determination of the superiority of the active treatments over placebo.

Per-Protocol (PP) Population includes all mITT subjects who applied their dispensed treatment, had no protocol deviations which could have interfered with the accurate assessment of treatment efficacy, and returned for the Day 15 visit within the allowed window. This is the primary population for the efficacy comparisons between the two active treatment groups.

Subjects whose condition worsens and require alternate or supplemental therapy for the treatment of head lice during the study will be discontinued, included in both the mITT and PP population analyses as treatment failures. Subjects who discontinue early for reasons other than treatment failure will be excluded from the PP population, but included in the mITT population. Last Observation Carried Forward (LOCF) will be used to impute any missing endpoints.

Efficacy analyses will be performed on both the per-protocol population and the mITT population. Safety analyses will be performed using the Safety population as defined.

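### AEs are summarized by randomized assignment in everyone dispensed a tube, so known non-appliers stay in the denominator and AEs after a dispensing error go to the product not received; the likely effect is small and cheap to fix.

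*SAP*

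**What the plan says.** **Grouping.** SAP 5 states that treatment group "refers to randomized treatment assignment: active-test, active-reference, and placebo". The introduction to Protocol 10 has the same definition. Protocol 10.4.3 and SAP 5.4 and 5.4.1 summarize AEs by treatment group. SAP 3.2 adds: "The randomization scheme for treatment allocation will be used for statistical and reporting purposes". Neither document makes an exception for safety.

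**Population.** The Safety population in SAP 4 "includes all subjects who were randomized and dispensed treatment", and Protocol 10.2 agrees. SAP 4 closes with: "Safety analyses will be performed using the Safety population as defined". Application is not required. The PP population does require it: it "includes all mITT subjects who applied their dispensed treatment".

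**Exposure.** Protocol 4.1 and SAP 1.1 describe a single application at home. Protocol 6.1.7 does not allow the dispensed product to be opened at the center. Protocol 8.3 starts the AE reporting period at first application, and SAP 3.4.3 defines a treatment-emergent AE as "any adverse event occurring on or after the initiation of study treatment".

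**Dispensing errors.** Protocol 6.2 tells sites to contact the CRA "in case of any dispensing errors or if discrepancies are discovered". No analysis rule follows from this.

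**The concern.** Two consequences follow from these definitions together.

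- **Denominator.** Being handed a tube is not exposure when the tube is used later at home. A child known not to have used it cannot have a treatment-emergent AE under the SAP's own definition, yet counts in any AE table that uses the Safety N.
- **Attribution.** A child assigned to one product and given another is counted under the assigned product. For mITT efficacy that is the right convention. For a safety table it credits the event to a product the child did not receive.

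The secondary objective is comparative safety and local tolerability of Test against Reference (SAP 2). Non-application at a similar rate in each arm shrinks absolute AE rates and their differences. Swaps between arms also shrink differences.

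**Working it through.** The plan gives no rate for non-application or dispensing errors, so there is no safety figure to reproduce. The power statement in Protocol 10.5 and SAP 3.1 does not depend on the safety rules; it reproduces at about 81.5% against the stated minimum of 80%.

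**Inputs**
- Arm sizes: 280 index subjects at 3:3:1 (Protocol 4.1) give 280 × 3/7 = 120 per active arm and 280/7 = 40 on placebo, matching SAP 3.1.
- Known reactions: each below 1% (Protocol 2.3.1).
- Assumed: share *f* who never apply, 1% to 10%; number *m* of wrong tubes, 1 to 3; AE tables use the Safety N, because the SAP does not name the denominator table by table.

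**1. Dilution.** Reported rate = *r* × (1 − *f*). For a true rate *r* = 5%:
- *f* = 1%: 5% × 0.99 = 4.95%
- *f* = 5%: 5% × 0.95 = 4.75%
- *f* = 10%: 5% × 0.90 = 4.5%

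With the same *f* in two arms, the ratio is *r*₁(1 − *f*) / [*r*₂(1 − *f*)] = *r*₁/*r*₂, so it does not change. The difference is multiplied by (1 − *f*). In counts, six affected children are 6/120 = 5.00% as planned. If 12 of the 120 never applied, they are 6/108 = 5.56% of those exposed.

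**2. One AE charged to the wrong arm**
- Placebo: 1/40 = 2.5 points
- Either active arm: 1/120 = 0.83 points

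**3. Swaps.** If *m* subjects in each of two arms receive the other arm's product, the AE-rate difference is multiplied by 1 − *m*/n₁ − *m*/n₂.
- Test and Placebo: the loss is *m* × (1/120 + 1/40), which is 3.3%, 6.7% and 10% of the difference for *m* = 1, 2, 3.
- Test and Reference: the loss is *m* × (1/120 + 1/120), which is 1.7%, 3.3% and 5%.

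Example with assumed rates of 10% on Test and 2% on Placebo and one swap: Test reads (119 × 10% + 2%)/120 = 9.93%, and Placebo reads (39 × 2% + 10%)/40 = 2.2%. The difference is 7.73 points instead of 8.

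**4. Expected size for a listed reaction.** Take three active tubes given to placebo-assigned children and a 1% reaction rate, which is the ceiling in Protocol 2.3.1. Expected misattributed events are 3 × 0.01 = 0.03, and 0.03/40 moves the placebo rate by 0.075 points.

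**The case against.** The best defense is that little turns on this. Safety reporting is descriptive (Protocol 10.4.3, SAP 5.4), with no test or margin. Planned listings cover PP exclusions, protocol deviations, drug accountability, diary data and all AEs (SAP 8), so affected children can be traced. A dispensed-based population also avoids relying on diaries to prove exposure. All of this stands as a limit on size. But listings do not correct the summary tables, and the diary argument covers only children whose status is unknown, not those documented as never having applied.

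A reader might infer more than the documents support:

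- **That wrong tubes are likely.** Protocol 6.2 treats errors as a contingency. Labels are blank and opaque and packaging is similar (Protocol 6.1.7). Against that, SAP 3.2 provides a computerized scheme from a third party, unblinded site personnel and an unblinded monitor, and Protocol 6.2 has the CRA reconcile drug accountability.
- **That contamination would swamp the known reactions.** One to three wrong tubes are 2.5% to 7.5% of the placebo arm, but that share is not comparable with reaction rates below 1%. The bias depends on their product, as in step 4.
- **That every safety measure is diluted.** Tolerability is analyzed in mITT and PP (SAP 5.3). PP requires application, so its tables are not diluted. mITT does not state that requirement, but it does need a post-treatment evaluation.
- **That a reporting cut-off will be crossed.** Six of 120 fails the above-5% rule of SAP Table 27 while 6/108 passes it, but only at that exact count. The protocol synopsis uses at least 5%, which 6/120 already meets.

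**Conclusion.** The point holds as a defect in a stated rule, with a small expected effect. Under the current text, AEs after a dispensing error are attributed to the product not received, and known non-appliers remain in the denominator of Safety-population AE tables.

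The size rests on assumed rates and on AE tables using the Safety N. With 1% to 10% non-application, a 5% rate falls by 0.05 to 0.5 points. The 10% end is illustrative; nothing in the documents suggests documented non-application would reach it. If non-application differed between arms, rate ratios would shift too, in a direction that cannot be predicted. A single misattributed event is most visible in the placebo arm, at 2.5 points.

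The documents do not support a claim that the safety comparison is materially biased. Efficacy by randomized assignment is not at fault.

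**What to change.** Settle this before unblinding, so that the grouping is not chosen with results in view. In Protocol 10.2 and SAP 4, 5 and 5.4:

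- Define the Safety population as randomized subjects who applied any study lotion. Exclude only documented non-appliers, and count unknown status as applied.
- Summarize safety by the product actually received. State this as an exception to the general treatment-group definition, and qualify the matching sentence in SAP 3.2.
- Keep randomized assignment for mITT efficacy.
- Flag dispensing errors and documented non-appliers in the existing listings.

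The cost is a wording change and one or two derived variables. Application status can come from the diary entries (Protocol 6.1.9) and returned tubes (Protocol 6.2). Product received must be confirmed from accountability and randomization records together, because Protocol 6.2 does not say that the log holds product identity in a form ready for analysis. The safety denominator becomes slightly smaller.

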5.1. Subject Disposition, Demographic and Baseline Characteristics

Subject disposition, including the number of subjects who completed the study, discontinued from the study, reasons for early discontinuation, and the number of days on study will also be provided and presented for all subjects randomized. Subject disposition will be summarized by treatment group.

Demographic data and baseline characteristics including age, ethnicity, race, gender, severity of itching and stinging/burning sensations, and skin/scalp irritation assessment will be summarized using appropriate descriptive statistics by treatment group for the mITT and PP populations. Descriptive statistics will be generated for continuous variables (e.g. age). The number and percentage of subjects in each class of categorical demographic and Baseline variables (e.g. gender, ethnicity, race, severity of itching and stinging/burning sensation; skin/scalp irritation assessment) will be tabulated by treatment group and population (mITT and PP) for Baseline (Visit 1). Individual subject demographic and Baseline characteristics data will be listed. No inferential testing will be performed.

5.2. Efficacy Analyses

5.2.1. Primary Efficacy Endpoint

The primary efficacy endpoint is the proportion of index subjects who are lice free (defined as no live lice, adults or nymphs) 14 days (Day 15) after treatment.

Descriptive statistics (number of subjects, number of subjects cured, and proportion of cured) for the primary efficacy variable will be tabulated by treatment group and population (mITT and PP).

5.2.2. Primary Efficacy Analyses

Bioequivalence assessment will be evaluated by comparing proportions of patients successfully cured in the test and the reference treatment groups. Bioequivalence between the test and the reference product will be established if the continuity-corrected 90% confidence interval for the difference in cure proportions between test and reference treatment is contained between the equivalence limits [-0.20, +0.20]. The hypothesis testing for the two, one-sided tests will be conducted using a 5% level of significance.

In this case, the compound two, one-sided tests hypothesis is:

 $H_0: p_T - p_R < -0.20 \text{ or } p_T - p_R > 0.20$ (meaning test product is not bioequivalent to the reference);

H_A: $-0.20 \le p_T - p_R \le 0.20$ (supporting bioequivalence);

where p_T = cure rate of test treatment, p_R = cure rate of reference treatment.

Let n_T = sample size of test treatment group, n_R = sample size of reference treatment group and se = $(\widehat{p_T}(1-\widehat{p_T})/n_T + \widehat{p_R}(1-\widehat{p_R})/n_R)^{\frac{1}{2}}$.

The 90% confidence interval will be estimated as follows, using Yates correction:

$$L = (\hat{p}_T - \hat{p}_R) - 1.645 \times se - (\frac{1}{n_T} + \frac{1}{n_R})/2$$
$$U = (\hat{p}_T - \hat{p}_R) + 1.645 \times se + (\frac{1}{n_T} + \frac{1}{n_R})/2$$

 H_0 is rejected if $L \ge -0.20$ and $U \le 0.20$ resulting in accepting H_A and concluding bioequivalence of the two products.

The primary endpoint is the evaluation at Day 15. The bioequivalence results in the PP population will be considered definitive, with those in the mITT population as supportive.

The following SAS code will be used for testing bioequivalence:

```
proc freq data = dataset;
    weight count;
    tables treat*outcome/ riskdiffc (equiv);
run;
```

The efficacy assessments for each active treatment vs. the Placebo will be conducted using twosided, continuity corrected Z-tests based on the following hypotheses:

Ho: $\pi_T = \pi_P$ Ha: $\pi_T \neq \pi_P$

CONFIDENTIAL

where,

 π_T , π_R , and π_P = the true cure proportions for Test, Reference, and Placebo treatments, respectively.

If both null hypotheses are rejected (p<0.05) and the observed cure proportions for the Test and Reference treatments are greater than that for the Placebo, then Superiority will be considered to have been demonstrated.

The superiority results in the mITT population will be considered definitive, with those in the PP population considered supportive.

5.2.3. Secondary Efficacy Endpoints

The secondary efficacy endpoint is the number and percentage of all index subjects who are licefree at Day 2. Descriptive statistics (number of subjects, number of subjects cured, and proportion cured) for the secondary efficacy variable will be tabulated by treatment group and population (mITT and PP).

5.2.4. Secondary Efficacy Analyses

As a secondary endpoint evaluation, patients' clinical progress at Visit 4 (Day 14) will be assessed and proportion of cured patients in treatment arms will be compared using the procedures described in the analysis of the primary efficacy endpoint.

5.3. Tolerability Assessment

Subjects' self-assessment of itching and stinging/ burning sensations during screening and treatment periods (Visits 2 through 5), skin/scalp irritation assessment by clinical site personnel (Visits 2 through 5), and ocular irritation assessment (Visits 3 through 5) by clinical site personnel will used to assess tolerability to the study treatments. Itching is defined as intense, distracting irritation or tickling sensation in the last 24 hours and is evaluated on a scale from 0 (No Itching) to 3 (Severe Itch). Stinging/ burning is defined as sensation of the skin is painfully hot or noticeable tingling sensation in the last 24 hours and is evaluated on a scale from 0 (Absent) to 3 (Severe). Skin/Scalp irritation is evaluated on a scale from 0 (None) to 3 (Severe) for four types of irritation including Pruritus= Itching, Erythema= Redness of the scalp, Excoriation= Breaking of the skin, usually caused by scratching, Pyoderma= Sores filled with clear fluid, pus or crusting. Each type of irritation is evaluated separately and its total score is recorded. Ocular irritation is evaluated for the presence of eye irritation, Conjunctivitis, and Ocular Hyperemia on a scale from 0 (No) to 1 (Yes).

Descriptive statistics using categorical methods will be used to compare tolerability measures between the test and reference treatment groups and various study days (e.g. Baseline (Visit 2), Visit 3, Visit 4, and Visit 5). Tolerability analyses will be presented for mITT and PP populations.

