7.3.2 Enrollment/Baseline

Enrollment/Baseline Visit Day 1 (Visit 1/ Visit 2)

- Review concomitant and prohibited medications.
- Record vital signs, results of examinations, other assessments.
- Perform assessment for living head lice on index subject and household members (up to 3 per household) for visual confirmation of infestation for a minimum of 15 minutes.
- Provide Standard of Care treatment on-site to infested household members (up to 3 per household).
- Randomize the index subject.
- Provide the study treatment for index subject.
- Provide index subject with subject diary and homecare instructions.
- Record Subject Self-Assessment for index subjects.
- Inform index subject when to come back for their first follow-up visit.

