7.3.3 Follow-up

Follow-up Visit Day 2 (Visit 3) (+/- 1 Day)

- Record adverse events as reported by participant or observed by investigator.
- Collect used test tube product from index subject.
- Concomitant and prohibited medication review.
- Perform assessment for living head lice on index subject for visual confirmation of infestation for a minimum of 15 minutes.
- If active lice are present on index subject, provide Standard of Care and withdraw the subject from the study.
- Record Subject Self-Assessment for index subjects.
- Perform skin/scalp irritation and ocular irritation for index subjects and record results on Site Assessment form.
- Record index subject's adherence to treatment program through collection of subject diary.
- Inform index subject when to come back for their follow-up visit.

Follow-up Visit Day 8 (Visit 4) (+/- 2 day)

- Record adverse events as reported by participant or observed by investigator.
- Concomitant and prohibited medication review.
- Perform assessment for living head lice on index subject for visual confirmation of infestation for a minimum
 of 15 minutes.
- If active lice are present, provide Standard of Care and withdraw the subject from the study.
- Record Subject Self-Assessment for index subjects.
- Perform skin/scalp irritation and ocular irritation for index subjects and record results on Site Assessment form.
- Inform index subject when to come back for their final study visit.

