16.1 Schedule of Events

TO.1 Scriedale of LV					
Visit Number	Visit 1 Screening ¹	Visit 2 Baseline ²	Visit 3 Follow-up	Visit 4 Follow-up	Visit 5 EOS/ET³
Visit Day	Day -1 to 0	Day 1	Day 2 ⁴	Day 8 (±2)	Day 15 (±3)
Informed Consent	Х				
Eligibility Criteria	Х				
Subject Demographics	Х				
Medical History	Х				
Physical Examination	X 5				
Investigational Product Dispensation/Randomization		X ₆			
Vital Signs ⁷		х			х
Urine Pregnancy Test ⁸	Х				x
Head Lice Visual Assessment	X ⁹	X ⁹	Х	Х	х
Household Members Standard of Care Treatment		х			
Local Skin/Scalp Irritation Assessment			х	Х	х
Ocular Irritation Assessment			Х	X	х
Subject Self-Assessment		X	Х	X	х
Investigational Product Accountability			x		
Subject Diary Dispensation		х			
Subject Diary Collection and Compliance Review			х		
Concomitant and Prohibited Medication Review	х	х	х	Х	х
Adverse Events Assessment			X ¹⁰	Х	х

¹ Rescreening will be permitted for out of window index subjects and those subjects whose household members cannot accompany them at their initial screening visit.

² Visit 2 (Baseline) may be completed on the same day as visit 1 (Screening). If Screening and Baseline are completed on the same day, assessments performed on both Screening and Baseline need only be performed once. Refer to Section 7. Study Procedures and Schedule of Events for details and restrictions.

³ Index subjects identified as treatment failures will be terminate early from the study and be provided the standard of care rescue treatment.

 $^{^{\}rm 4}$ Must be within 24 hours of treatment.

⁵ Physical examinations are to be performed if Inclusion/Exclusion Criteria are satisfied at Screening.

⁶ Prior to Randomization, the Investigator must confirm the subject still meets all Inclusion/Exclusion Criteria.

⁷ Vital signs will include body temperature, heart rate and blood pressure (systolic and diastolic). Blood pressure and heart rate will be measured after the subject has been sitting restfully for at least 5 minutes.

⁸ For female index subjects of child-bearing potential.

⁹ For both index subjects and infested household members.

¹⁰ AE reporting period for this study begins upon receiving the first application of investigational product and ends at the final protocol required visit.

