8. TABLES, LISTINGS AND FIGURES

Tables

- 1. Summary of Subject Enrollment and Disposition.
- 2. Summary of Subject Demographics at Screening (mITT population).
- 3. Summary of Subject Demographics at Screening (PP Population).
- 4. Summary of Medical History/Other Concomitant Illness at Screening.
- 5. Summary of Physical Exam Abnormalities.
- 6. The Difference in proportion of patients that are identified as cured on Study Day 15 (Visit 5) Treated with Ivermectin and Sklice (mITT population).
- 7. The Difference in proportion of patients that are identified as cured on Study Day 15 (Visit 5) Treated with Ivermectin and Sklice visit (PP population).
- 8. The Difference in proportion of patients that are identified as cured on Study Day 15 (Visit 5) Treated with Ivermectin Vs Placebo and Sklice Vs Placebo (mITT population).
- 9. The Difference in proportion of patients that are identified as cured on Study Day 15 (Visit 5) Treated with Ivermectin Vs Placebo and Sklice Vs Placebo (PP population).
- 10. Summary of Head Lice visual examination at each visit (mITT population).
- 11. Summary of Head Lice visual examination at each visit (PP Population).
- 12. The Difference in proportion of patients that are identified as cured on Study Day 2 (Visit 3) Treated with Ivermectin and Sklice (mITT population).
- 13. The Difference in proportion of patients that are identified as cured on Study Day 2 (Visit 3) Treated with Ivermectin and Sklice (PP population).
- 14. The Difference in proportion of patients that are identified as cured on Study Day 2 (Visit 3) Treated with Ivermectin Vs Placebo and Sklice Vs Placebo (mITT population).
- 15. The Difference in proportion of patients that are identified as cured on Study Day 2 (Visit 3) Treated with Ivermectin Vs Placebo and Sklice Vs Placebo (PP population).
- 16. Summary of self-assessment of itching and stinging/ burning sensations at each visit (mITT population).
- 17. Summary of self-assessment of itching and stinging/ burning sensations at each visit (PP population).
- 18. Summary of change of self-assessment of itching and stinging/ burning sensations from baseline at each visit (mITT population).
- 19. Summary of change of self-assessment of itching and stinging/ burning sensations from baseline at each visit (PP population).
- 20. Summary of local skin/scalp irritation assessment at each visit (mITT population).
- 21. Summary of local skin/scalp irritation assessment at each visit (PP population).

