- 22. Summary of ocular irritation assessment at each visit (mITT population).
- 23. Summary of ocular irritation assessment at each visit (PP population).
- 24. Summary of change of local skin/scalp irritation assessment from baseline at each visit (mITT population).
- 25. Summary of change of local skin/scalp irritation assessment from baseline at each visit (PP population).
- 26. Adverse Events by System Organ Class and Preferred Term.
- 27. Adverse Events with incidence >5 % by System Organ Class and Preferred Term.

- 28. Treatment Emergent Adverse Events by System Organ Class and Preferred Term.
- 29. Treatment Emergent Adverse Events by maximum Severity.
- 30. Summary of Treatment Emergent Adverse Events possible or probably related to the study drug.
- 31. Summary of Serious Adverse Events by System Organ Class and Preferred Term.
- 32. Summary of Concomitant Medications.

Data Listings

- 1. Listing of Analysis Population and Study Completion.
- 2. Listing of Subjects Who Discontinued.
- 3. Listing of Patients Excluded from Per Protocol Efficacy Analysis.
- 4. Listing of Protocol Deviation.
- 5. Listing of Subject Demographics.
- 6. Listing of Drug Accountability.
- 7. Listing of Head Lice visual examination of index subjects.
- 8. Listing of Head Lice visual examination of house hold members.
- 9. Listing of Subject Diary data.
- 10. Listing of Patient Self-assessment.
- 11. Listing of local skin/scalp irritation assessment.
- 12. Listing of ocular irritation assessment.
- 13. Listing of Adverse Events.
- 14. Listing of Treatment Emergent Adverse Events.
- 15. Listing of Non-Treatment Emergent Adverse Events.
- 16. Listing of Adverse drug reaction.
- 17. Listing of Treatment Emergent Adverse Events which lead to discontinuation of study treatment.
- 18. Listing of Non-Treatment Emergent Adverse Events which lead to discontinuation of study treatment.
- 19. Listing of Treatment Emergent Adverse Events which lead to Withdrawal from the study.
- 20. Listing of Non-Treatment Emergent Adverse Events which lead to Withdrawal from the study.
- 21. Listing of Concomitant Medication.
- 22. Listing of Serious Adverse Events.
- 23. Listing of Serious Adverse Events with fatal outcome.
- 24. Listing of Medical History.
- 25. Listing of Physical Examination.
- 26. Listing of Pregnancy test.
- 27. Listing of Subject Vital Signs for Randomized Population.
- 28. Listing of Inclusion/Exclusion Criteria (Randomized Population).

Figures

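### The SAP uses a baseline skin/scalp irritation score, but neither schedule requires that assessment before treatment

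*SAP*

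**What the plan says.** Three places in the SAP assume a skin/scalp irritation score taken before treatment.

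- SAP 5.3 lists, among the tolerability data, "skin/scalp irritation assessment by clinical site personnel (Visits 2 through 5", and compares "various study days (e.g. Baseline (Visit 2), Visit 3, Visit 4, and Visit 5".
- SAP 5.1 includes the assessment among the baseline characteristics, which "will be tabulated by treatment group and population (mITT and PP) for Baseline (Visit 1".
- SAP 8 plans Table 24, "Summary of change of local skin/scalp irritation assessment from baseline at each visit (mITT population", and Table 25, its per-protocol counterpart. Tables 20 and 21 are by-visit summaries; Table 20 is titled "Summary of local skin/scalp irritation assessment at each visit (mITT population". Figures 7 and 8 plot the same data.

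The collection plan is different. In Protocol 16.1 and again in SAP 1.2, the row "Local Skin/Scalp Irritation Assessment" is blank at Visits 1 and 2 and marked at Visits 3, 4 and 5. Protocol 7.3.3 instructs sites at Day 2 and Day 8 to "Perform skin/scalp irritation and ocular irritation for index subjects and record results on Site Assessment form", and Protocol 7.3.4 repeats this for Day 15. The screening and baseline lists (Protocol 7.3.1 and 7.3.2) do not name the assessment.

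**The concern.** A site that follows the protocol exactly produces no baseline score for pruritus, erythema, excoriation or pyoderma. The SAP 5.1 baseline rows, any Visit 2 rows in Tables 20 and 21, and all of Tables 24 and 25 then have no required source data. If some sites complete the grid at baseline and others do not, Tables 24 and 25 would describe a subset selected by site practice.

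This matters because head lice themselves irritate the scalp. Exclusion criterion 4 removes only skin or scalp conditions that are not due to the infestation, so lice-related irritation can be present at entry. Without a pre-treatment score, it cannot be reliably separated within a subject from irritation that appears after the lotion. Local tolerability against the reference product is part of the secondary objective, and a score not taken before treatment cannot be recovered later.

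**Working it through.** No power, margin or rate is involved. The check sets the planned analyses beside the planned collection.

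**Step 1. Visits by instrument.** SAP 5.3 is compared with the rows in Protocol 16.1 and SAP 1.2, which agree with each other.

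| Instrument | Visits in SAP 5.3 | Visits marked in both schedules | Unmatched |
|---|---|---|---|
| Self-assessment (itching, stinging/burning) | 2, 3, 4, 5 (4) | 2, 3, 4, 5 (4) | 0 |
| Skin/scalp irritation | 2, 3, 4, 5 (4) | 3, 4, 5 (3) | 1 (Visit 2) |
| Ocular irritation | 3, 4, 5 (3) | 3, 4, 5 (3) | 0 |
| Total | 11 | 10 | 11 − 10 = 1 |

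The single mismatch is skin/scalp irritation at Visit 2. Pre-treatment visits with the assessment scheduled: 0 of 2. Post-treatment visits: 3 of 3.

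**Step 2. Could another instruction supply the score?**

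- *Site Assessment form.* Protocol 7.1.1 sends lice results to this form, and lice are examined at Visits 1 and 2. Protocol 16.4 shows the four-sign grid on the same form. A site could complete the grid then, but no instruction tells it to.
- *Baseline list.* Protocol 7.3.2 has a general line covering examinations and other assessments, without naming this one.
- *Physical examination.* Protocol 7.1 includes skin at screening, but not the 0–3 grid.
- *Exclusion criterion 4.* It refers to an erythema score, so one of the four signs has a reason to be looked at for eligibility.
- *Self-assessment.* Itching is scored at Visit 2 on a 0–3 scale almost identical to the pruritus column. It is a close substitute for that sign only.
- *eCRF.* SAP 1 refers the reader to it for data collection. It is not among the documents.

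Pruritus therefore has a scheduled substitute, erythema has only an eligibility check, and excoriation and pyoderma have nothing. None of these sources schedules all four signs before treatment.

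**Step 3. Outputs affected.** SAP 8 has ten tolerability tables, numbered 16 to 25.

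- Wholly dependent on the baseline score: Tables 24 and 25 (2).
- Dependent for any Visit 2 row: Tables 20 and 21 (2). Figures 7 and 8 are in the same position.
- Not dependent: Tables 16, 17, 18, 19, 22 and 23 (6).
- Check: 2 + 2 + 6 = 10.

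**Step 4. Which visit is Baseline?** SAP 5.1 labels it Visit 1. SAP 5.3 and both schedules put it at Visit 2 (Day 1), in line with SAP 3.4.3, which equates Baseline with Treatment Day 1. The Visit 1 label probably reflects the permitted same-day visits, since Protocol 7.3.2 is headed "Enrollment/Baseline Visit Day 1 (Visit 1/ Visit 2". This is a labelling slip of little consequence, and the assessment is unmarked at both visits.

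**The case against.** The strongest reply accepts the mismatch and disputes its weight.

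- *The protocol's tolerability analysis does not need the score.* The Synopsis bases it on stinging/burning and itching at follow-up, test against reference. Randomisation deals with pre-existing irritation in that comparison, and both symptoms have a scheduled Visit 2 value. This stands, and it limits the point to the SAP's own baseline and change-from-baseline outputs.
- *The eCRF may already collect it.* SAP 5.3 gives ocular irritation a later first visit than skin/scalp irritation, and SAP 8 plans change tables for one but not the other. That looks as much like deliberate drafting as a slip. The documents cannot settle this. Even so, the schedules and visit lists would still not ask for the score, so complete collection at every site could not be assumed.
- *A sparse table would show its own n.* SAP 7 requires the contributing number to be shown and leaves missing data out of percentages; SAP 3.4.2 rules out imputing safety data. This makes the gap visible, but it neither restores the scores nor removes selection by site.
- *An amendment is heavy for two descriptive tables.* That is a fair argument for preferring the SAP-only correction. It is not an argument for leaving the documents in conflict.

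**Conclusion.** The concern holds. As written, the SAP plans baseline and change-from-baseline summaries of skin/scalp irritation for which neither the protocol nor the SAP's own schedule requires a pre-treatment score. The mismatch is 1 of 11 assessment-visits. It affects Tables 24 and 25 entirely, any Visit 2 content in Tables 20 and 21 and Figures 7 and 8, and the skin/scalp rows in the SAP 5.1 baseline summary.

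How many subjects would lack the score cannot be known from the documents; it depends on the eCRF and on site practice. The outputs may therefore be empty, partly filled or, if the eCRF collects the grid and sites complete it, full.

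Only descriptive tolerability outputs and baseline rows are affected. The efficacy analyses, the sample size, the self-assessment tables and the between-arm comparisons at follow-up are not. The point should be corrected, but it does not threaten the trial's main conclusions.

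**What to change.** Choose one of two routes.

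1. **Collect the score.** Mark the skin/scalp assessment at Visit 2, before study drug is dispensed, in Protocol 16.1 and SAP 1.2, and name it in Protocol 7.3.2 using the four-sign grid already on the Site Assessment form. If the eCRF already collects it, the schedules should still say so, so that every site completes it. *Cost:* a protocol amendment with prospective IRB approval (Protocol 12.2), a SAP change and possibly an eCRF change. The site work is one more section of a form already used for that visit's lice check. Subjects enrolled earlier would lack the score unless their site happened to record it, so change from baseline would mainly cover later enrollees.

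2. **Withdraw the baseline use.** Remove skin/scalp irritation from the SAP 5.1 baseline list, change its visits in SAP 5.3 to 3 through 5, limit Tables 20 and 21 and Figures 7 and 8 to those visits, and delete Tables 24 and 25. *Cost:* SAP wording only, at the price of giving up the within-subject comparison.

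Under either route, change the Baseline label in SAP 5.1 to Visit 2 (Day 1), noting that this may fall on the same day as Visit 1.
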